### **9.6.4. Reuse Risk**

All study devices will be single patient use.

### **9.6.5. Sterilization Risk**

The following devices will be supplied sterilized:

- Infusion sets
- Insulin reservoirs
- Glucose sensors

### **9.6.6. Misuse Risk**

Comprehensive training will take place at the initiation visit for investigational center staff for all the devices being used, to include all of its functional components and all other study devices to be used during the study at the investigational center.

### **9.6.7. Risk of Blood Sample Collection, Contamination from Sampling Techniques**

Detailed mitigations to blood sampling risk are provided in Section 10.

## **9.7. Glucose and Glycemia Measurements**

During the course of the study, the subjects' BG levels, SG levels, and blood ketones will be assessed using the methods outlined in this section.

### **9.7.1. Daily Blood Glucose**

Values will be assessed during the study by all subjects using the CONTOUR® NEXT LINK 2.4 study meter. The control solution test will be performed following the manufacturer's user guide. Subjects will be trained on the use of the CONTOUR® NEXT LINK 2.4 study meter per the manufacturer's instructions.

### **9.7.2. Sensor Glucose Values**

SG data will be collected by subject's study insulin pump and calibrated by each subject's CONTOUR® NEXT LINK 2.4 study meter.

## **9.8. Recording Data**

Data will be captured on eCRFs using OC-RDC module. Original eCRFs will not be considered as source data and supporting documentation will be required.

Electronic device data will be collected from the study pump using CareLink™ Personal For Clinical Research software. The system uses TLS technology, which encrypts all data it stores (21 CFR Part 11 compliant). Certain data points stored in the downloaded information may also be captured on the appropriate eCRF.

The investigator will ensure that all eCRFs are completed promptly, completely, and accurately. Medtronic will provide detailed instructions to assist with eCRF completion. In the event of data discrepancies, investigational centers will be asked to resolve queries electronically in the OC-RDC system; otherwise, irresolvable data-related issues will be routed to the sponsor for review and final disposition. An audit trail is maintained in OC-RDC to capture any corrections or changes of the eCRFs. System backups for data stored in the Oracle Clinical system will be consistent with Medtronic Standard Operating Procedures (SOPs).

Medtronic will only consider eCRFs to be complete when all discrepancies between source data and eCRF have been resolved and eCRF content has been reviewed by a study monitor. In addition, specific eCRFs must also be reviewed and electronically signed by the investigator, indicating his/her agreement with the accuracy of all recorded data. It is expected that the investigator and his/her staff will cooperate with the monitoring team and provide any missing data in a timely manner.

## **9.9. Deviation Handling**

A deviation is any instance(s) of failure to follow, intentionally or unintentionally, the requirements of the CIP. It is expected that the investigator will conduct this clinical trial in compliance with the CIP and all applicable regulations governing the conduct of clinical research involving human subjects. Failure to do so could result in one or all of the following:

- Investigational center disqualification
- Notification to the regulatory authorities/IRB depending on the severity of the deviation and reporting requirements

The investigator should not implement any deviation from, or changes to, the CIP without agreement by the sponsor and prior review and documented approval/favorable opinion from the IRB, except where

necessary to eliminate an immediate hazard(s) to trial subjects or when the change does not affect the scientific soundness of the plan or the rights, safety, and welfare of the subjects.

The following are deviations related to study procedures:

- If subjects do not follow the fingerstick recommendations, no study deviation will be given unless the site staff did not train the subject on SMBG study procedures.
- If subjects do not upload devices perfectly, no study deviation will be given unless the site staff did not train the subject on upload procedures.
- As it can occur that subjects do not follow study instructions perfectly, such as uploading their pumps, changing between Auto Mode and Manual Mode, no study deviation will be given unless site staff did not provide sufficient instructions to subjects regarding study requirements.
- If subject does not collect enough blinded CGM data during the run-in period, no study deviation will be given as long as subject made effort to wear the blinded CGM.

## FST Sample:

Deviations for missing ABL-90 FST samples will be issued for the following reason: If there are 3 or more total ABL-90 FST samples missing per subject per SMBG FST (unless they were missed for safety issues, IV or FST device issues).

### **9.9.1. Unplanned CIP Deviations**

The investigator may encounter the need to deviate from the CIP when necessary to protect the safety, rights or well-being of a subject in an emergency or in unforeseen situations beyond the investigator's control (e.g. subject failure to attend scheduled follow-up visits, inadvertent loss of data due to computer malfunction, inability to perform required procedures due to subject illness).

All deviation from the CIP, regardless of the reason should be documented as soon as possible, after the deviation occurs or is identified. This documentation should include deviation date, description of the deviation, and the reason for deviation.

CIP deviations should be reported as follows:

- a) To the IRB for notification/acknowledgement, if required;
- b) To the sponsor and, if required;
- c) To the applicable regulatory agency (reported by the sponsor)

For medically justifiable conditions that preempt a subject's ability to complete a study-required procedure, it may be permitted to report only one deviation that will apply to all visits going forward. This may also apply to other unforeseen situations (e.g. the subject permanently refuses to complete a study required procedure and the data will not contribute to the primary end point analysis). However, prior approval from sponsor is required for such situations.

### **9.9.2. Minor or Administrative CIP deviations**

Minor or administrative deviations are those that do not "affect the scientific soundness of the research plan or the rights, safety, or welfare of human subjects."

Deviations that do not meet the criteria for expedited notification or prior regulatory/IRB approval, may be reported at the time of eCRF completion or separately upon discovery such as during monitoring visits.

If a CIP deviation occurs which meets this definition, the deviation should be reported to the IRB at the time the continuing review application is submitted.

### **9.9.3. Reporting Requirements for Study Deviations**

All study deviations must be reported on the eCRF regardless of whether medically justifiable, an inadvertent occurrence, or taken to protect the subject in an emergency. The date and reason for each deviation will be documented (21 CFR 812.140 Records). In the occurrence of a corrupted device interrogation file, Sponsor may request a deviation to document that a readable interrogation file is unavailable.

In order to protect the rights and interests, safety and health of subjects, the deviation occurred under emergency situations that cannot be timely reported shall be reported in written form afterwards in accordance with relevant regulations as soon as possible.

The following examples are deviations that could impact subject safety, affect the integrity of study data and/or affect subject's willingness to participate in the study. These deviations are significant and require immediate sponsor notification upon investigator awareness.:.

- Failure to obtain informed consent/assent, i.e., there is no documentation of informed consent/assent
- Informed consent/assent obtained after initiation of study procedures
- Continuation of a subject who did not meet all inclusion/exclusion criteria
- Performing study procedure not approved by the IRB
- Failure to inform IRB and sponsor of reportable AEs (see Section 11)
- Investigational study device dispensed without obtaining informed consent/assent

In the event the deviation involves a failure to obtain a subject's consent, or is made to protect the life or physical well-being of a subject in an emergency, the deviation must be reported to the IRB as well as Medtronic within five (5) working days.

Reporting of all other study deviations should comply with IRB policies and/or local laws and must be reported to Medtronic as soon as possible upon the center becoming aware of the deviation. Reporting of deviations must comply with IRB policies, local laws, and/or regulatory agency requirements. Refer to Investigator Reports, Table 7, for specific deviation reporting requirements and timeframes for reporting to Medtronic, IRB, and/or regulatory agency (if applicable).

### **9.9.4. Analyzing Deviations**

Medtronic is responsible for reviewing deviations, assessing their significance, and identifying any additional corrective and/or preventive actions (e.g. amend the CIP, conduct additional training, terminate the investigation). Repetitive or serious investigator compliance issues may result in initiation of a corrective action plan with the investigator and investigational center, and in some cases, necessitate suspending enrollment until the problem is resolved or ultimately terminating the investigator's participation in the study.

## 9.10. Subject Exit, Withdrawal or Discontinuation

Subjects may choose to withdraw from the study at any time by notifying investigational center staff of their intent.

If a subject chooses to end his or her study participation or if the subject is removed from the study at the Investigator's discretion or for failure to meet the study requirements, the reason for withdrawal must be documented. All study devices and supplies must be returned (as applicable) and documented both in source documents and on an eCRF.

Subjects may also be withdrawn from the study at the discretion of the Investigator. A subject will be withdrawn from the study if:

- In the opinion of the investigator, the subject's health or safety would be compromised by continuing in the study
- In the opinion of the investigator, it is in the subject's best interest to discontinue participation in the study
- During the course of the study, subject begins participation in another investigational study (drug or device).
- Subject participates in a phase that requires a Smartphone as part of the study requirements and subject does not have a Smartphone.
- During the course of the study, subject begins abusing illicit drugs.
- During the course of the study, subject begins abusing alcohol.
- During the course of the study, subject begins using pramlintide (Symlin), DPP-4 inhibitors, liraglutide (Victoza or other GLP-1 agonists), metformin, canagliflozin (Invokana or other SGLT2 inhibitors).
- During the course of the study, the subject demonstrates that he/she is not able to comprehend instructions for study procedures, as evaluated by the appropriate research staff.
- During the course of the study, subject is taking oral, injectable, or IV glucocorticoids
- During the study, (female) subject becomes pregnant.
- During the study, the subject experiences one severe hypoglycemic episode
- During the study, the subject experiences one episode of DKA
- During the study, subject has a cardiovascular event or any vascular event such as stroke.

Documentation of the reason(s) leading to subject withdrawal will be kept in the subject's source documentation.

For **Study Exit** visits for reason other than subject lost to follow-up, the following information is required:

- Assess and document any reportable AEs (refer to section 10 Adverse Events)
- For study exit visits occurring in the clinic, perform a CareLink™ upload
- If the study exit visit occurs via telephone, ensure the subject has completed a CareLink™ upload prior to the telephone follow-up

## 9.11. Subject Stopping Rules

Any episode of DKA or severe hypoglycemia will result in withdrawal of subject from study.

## 9.12. Stopping Rules for Entire Study

During the study period, the following steps will be taken for:

- Unanticipated Adverse Device Effects (UADE)
- Algorithm-related Diabetic Ketoacidosis (DKA)
- Algorithm-related Severe hypoglycemia

1. Site will notify the sponsor within approximately 24 hours of receiving knowledge of the event.
2. Sponsor will notify Food and Drug Administration (FDA) within approximately 72 hours of knowledge of the event and provide updates to those agencies as information becomes available.
3. Clinical Events Committee (CEC) is to review the event within 10 days from the time that the sponsor is notified.
4. CEC will provide recommendation to the sponsor on the following:
  - a) If enrollment and study may continue
  - b) If enrollment should be stopped; enrolled subjects are still allowed to continue in study
  - c) If the entire study must be stopped, including subjects who have already received study devices
5. The study will be suspended if 2 or more algorithm-related DKA events OR 4 or more algorithm-related Severe Hypoglycemia events occur

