### 9.2. Visit Schedule & Scheduled Follow-up Visit Windows

Each subject's participation will be comprised of the following scheduled visits listed below over the course of approximately 4.5 months during the run-in period and study period, and for 1 month during the interim period. With Sponsor and site approval, telemedicine (e.g., remote/virtual visit) may be performed for office visits that do not require any of the following:

- Collection of blood test samples
- Training
- Device related procedures that require staff assistance

The schedule is planned as follows:

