**Study Period Visits:**

- Visit 11 (Office or Telemedicine): Day 30 (+7 days) after Visit 3
  - Start Study Period
  - Retrieve insulin delivery device settings recommendations
  - Review/approve settings before programming pump (please note that investigator discretion may be used as described above)
  - Upload pump and meter during visit
  - Review CareLink™ Upload
  - Instruct subjects regarding study procedures for Challenge #1
- Visit 12 (Telephone): Day 1 after Visit 11
  - Review CareLink Upload
- Visit 13 (Telephone): Day 2 after Visit 11
  - Review CareLink™ Upload
- Visit 14 (Telephone): Day 7 (+2 days) after Visit 11
  - Review CareLink™ Upload
  - Instruct subjects to upload on Day 6 after Visit 14
- Visit 15 (Office or Telephone): Day 8 (+3 days) after Visit 14
  - Upload pump and meter during visit
  - Review CareLink™ Upload
  - Retrieve insulin delivery device settings recommendations
  - Review/approve settings before programming pump (please note that investigator discretion may be used as described above)
  - Program pump with insulin delivery settings
  - Instruct subjects to upload on Day 6 after Visit 15

- Visit 16 (Office or Telemedicine): Day 8 (+3 days) after Visit 15
  - Review CareLink™ Upload
  - Retrieve insulin delivery device settings recommendations
  - Review/approve settings before programming pump (please note that investigator discretion may be used as described above)
  - Program pump with insulin delivery settings
  - Instruct subjects to upload on Day 6 after Visit 16
- Visit 17 (Telephone): Day 8 (+3 days) after Visit 16
  - Review CareLink™ Upload
  - Retrieve insulin delivery device settings recommendations
  - Review/approve settings before programming pump (please note that investigator discretion may be used as described above)
  - Program pump with insulin delivery settings
- Visit 18 (Office or Telemedicine): Day 7 (+3 days) after Visit 17
  - Review CareLink™ Upload
  - End of Phase
  - Return AHCL system unless phase is repeated Review CareLink™ Upload

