## 9.13. Success Criteria for Feasibility 2 (Digital Twin and Meal Prediction)

The following criteria will be used to evaluate success of the Feasibility 2:

No occurrence of severe hypoglycemia or DKA due to device algorithm during the feasibility studies

1. Average time with SG below 70 mg/dL of 47 minutes or less (i.e.  $\leq 3.3\%$ ) as in CER294DOC

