## 12. Data Review Committees

### 12.1. Clinical Events Committee

A clinical events committee (CEC) consisting of external physicians with an expertise in endocrinology and the management of diabetes including insulin pumps and CGM will be convened. The CEC will review AEs as required per protocol, which include reports of:

- Serious Adverse Event
- Serious Adverse Device Effect
- Unanticipated Adverse Device Effect
- Severe Hypoglycemia
- Diabetic Ketoacidosis
- Severe Hyperglycemia

The CEC will assess events to determine agreement or disagreement with the investigator classification of an event. The CEC will only provide three causality assessments for device and procedure relatedness: Not Related, Possible, and Causal relationship.

If the CEC disagrees with the investigator's classification of the event, the rationale will be provided to the investigator. If the investigator agrees with the CEC's adjudication, the CRF documenting the AE will be updated accordingly.

If the investigator does not agree with the CEC's adjudication classification, both determinations will be provided within the final report; however, the CEC's adjudication will be used for data analysis. The disagreement will also be included in reporting to ECs and regulatory authorities, if required.

Causality Categories for Investigational Center	Causality Categories for CEC:

• Not Related

• Unlikely

• Possible

• Probable

• Causal relationship

	

• Not Related

• Possible

• Causal relationship

The sponsor will notify the investigator of any disagreement in assessment of an event by the CEC.

Refer to Section 9.12 for Stopping Rules for Entire Study and 10 day review requirements.

The CEC may review applicable information for device related AEs which may include:

- Whether or not the event was unanticipated
- Review of sensor data from CareLink™ Personal For Clinical Research software report (when applicable)
- Review of pump data from CareLink™ Personal For Clinical Research software report (when applicable)
- Misuse of the device by the user

Review of events may require the following information. Final disposition may be delayed based on obtaining this information:

- Monitoring by sponsor at site
- Device return and failure analysis

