- CareLink™ Personal For Clinical Research upload and review of CareLink™ Personal For Clinical Research software reports
- Subject clarification to site regarding details about the event

- Source documents that support event: Paramedic records; ER records; Lab records; Hospital admission and discharge summary

The following factors should be carefully considered in the CEC's recommendation to sponsor:

1. Was the severe hypoglycemia or DKA related to the AHCL algorithm, or was it related to a known insulin pump risk? For example, a question that may be considered in DKA would be whether the event was related to an infusion set issue or caused by the AHCL algorithm.
2. Another important consideration would be if the severe hypoglycemia, severe hyperglycemia or DKA event was related to a device malfunction versus patient non-compliance. For example, if a software anomaly leading to an under-delivery of insulin is discovered versus the subject repeatedly ignoring alarms prompting the subject to take action.
3. Severe hypoglycemia, severe hyperglycemia or DKA caused directly by an infusion set issue when the study pump is functioning as intended would likely result in acceptance to proceed with the study versus severe hypoglycemia or DKA that are directly caused by the AHCL algorithm or a device malfunction might stop study enrollment or entire study altogether.
4. It should be noted that the final determination of causality related to AHCL System that is made by the CEC may include additional factors which the members consider to be clinically relevant and important.

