## Sponsor's Support

The sponsor shall avoid improper influence on, or inducement to, the subject, monitor, any investigator(s) or other parties participating in or contributing to this study.

Sponsor representatives may provide support as required for the study, including technical support at investigational center. Sponsor representatives may provide technical support as required for the study under supervision of the PI, including:

- 1) Provide study training relevant and pertinent to the involvement of personnel conducting study activities and investigator responsibilities.
- 2) Technical support will be provided during study period.
- 3) Technical support will be under the supervision of a study investigator, but no data entry on the eCRF shall be performed by Medtronic personnel or their representatives at investigational centers.
- 4) Technical support to conduct device interrogations.

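### The study-wide stopping rules are worded to run only from Visit 11; the whole study is probably meant, and the lead-in phrase should say so

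*Protocol*

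**What the plan says.** Section 9.12 of the protocol, and the synopsis row on stopping rules for the entire study, begin: "During the study period, the following steps will be taken for" UADEs, algorithm-related DKA and algorithm-related severe hypoglycemia. Five numbered steps follow: site notice to the sponsor in about 24 hours, sponsor notice to FDA in about 72 hours, CEC review within 10 days, the CEC's recommendation, and suspension at 2 or more algorithm-related DKA events or 4 or more algorithm-related severe hypoglycemia events.

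The protocol uses the term study period for one segment of participation. In each Cohort A and Cohort C schedule in section 9.2.1, Visit 11 carries the item "Start Study Period". Section 9.2 describes participation "during the run-in period and study period, and for 1 month during the interim period", which keeps the three segments apart.

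The neighbouring success criterion in 9.13 uses a wider window: "No occurrence of severe hypoglycemia or DKA due to device algorithm during the feasibility studies". Section 12.1 sets no deadline of its own for the CEC and points back: "Refer to Section 9.12 for Stopping Rules for Entire Study and 10 day review requirements". The SAP contains no stopping rule.

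**The concern.** A stopping rule needs a clear time window, because someone has to decide whether a given event counts. As worded, this one starts at Visit 11, yet subjects are exposed well before then. Full Auto Mode (automated basal plus auto correction) is activated at Visit 3. In Challenge #2, all subjects deliberately miss a meal bolus every day of the run-in. Children aged 2-6 spend 5 in-clinic days in Auto Mode before they reach Visit 3. A repeated phase is preceded by a wash-out of at least 23 days in Auto Mode.

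Three provisions are at stake: the 72-hour FDA notice and the suspension count, which appear only in 9.12 and the synopsis, and the 10-day CEC deadline, for which 12.1 relies on 9.12. The 24-hour site report is not at stake, since section 11.4 asks for it (as the desired timing) without limiting it to a period.

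**Working it through.** The plan gives no figure on this point, so there is none to reproduce. The check has two parts: what the wording covers, and how much time lies outside it.

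**Wording.**
- Steps 1 to 5 share one lead-in. Step 5, the suspension count, has no time limit in its own sentence; it is limited only because it is one of the listed steps.
- The study period begins at Visit 11 in every schedule. The run-in and interim periods are named separately. The glossary does not define the term.
- 9.12 does not say which algorithm is meant by algorithm-related. Section 12.1 has the CEC ask: "Was the severe hypoglycemia or DKA related to the AHCL algorithm, or was it related to a known insulin pump risk". That points to AHCL, which is running from Visit 3 at the latest. UADEs in 9.12 carry no algorithm condition.

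**Time, from the visit windows in 9.2.1.**
- Visit 3 to Visit 11: day 30 (+7), so 30 to 37 days.
- Cohort A, Visit 11 to Visit 18: shortest 7 + 8 + 8 + 8 + 7 = 38 days; longest 9 + 11 + 11 + 11 + 10 = 52 days.
- Cohort C, Visit 11 to Visit 14: 42 to 49 days.

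Share of calendar days outside the literal window = (Visit 3 to Visit 11) / (Visit 3 to end of phase), one pass:

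| | Lowest | Nominal | Highest |
|---|---|---|---|
| Cohort A | 30/(30+52) = 36.6% | 30/(30+38) = 44.1% | 37/(37+38) = 49.3% |
| Cohort C | 30/(30+49) = 38.0% | 30/(30+42) = 41.7% | 37/(37+42) = 46.8% |

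Pump wear before Visit 3, the 5 in-clinic days for ages 2-6 and any wash-out come on top and are not in these shares.

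**Missed boluses in Challenge #2.** The run-in has about 23 planned missed-bolus days for everyone. Group 1 adds weeks 1 to 3 of the study period, about 21 days; Group 2 adds none. So about 23 of 44 planned days in Group 1 (52%), and all of them in Group 2, fall before the literal window.

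**If only the cloud algorithms count.** Digital Twin recommendations are first retrieved at Visit 11, and Cohort C subjects do not use the App in the run-in. For DKA and severe hypoglycemia, one pass then has 0 exposed days before Visit 11. The UADE trigger is still restricted.

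**The case against.** The strongest reply is that the section, read as a whole, already means the entire study. Its heading says so. Step 4(c) reaches subjects who already hold study devices, and devices are handed out at Visit 2 or 2A. Section 9.13 counts similar events across the feasibility studies. The protocol also uses the term loosely: under Sponsor's Support, "Technical support will be provided during study period" can hardly mean from Visit 11 only, and inclusion criterion 6 requires a night companion for the study period, while the version history describes that criterion as reducing risk during the study.

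Most of this stands as evidence of intent. It does not remove the ambiguity. Beside 9.11, which covers stopping for a subject, the heading of 9.12 may describe what is stopped rather than when the rule applies. Step 4(c) concerns the remedy, not the trigger. If the intent is the whole study, the lead-in is simply the wrong phrase.

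A reader might infer more, and the documents do not support it:
- *That the run-in has no safety oversight.* Adverse events are collected from consent (11.1). Severe hypoglycemia, DKA, SAEs and SADEs go to the sponsor, desired within 24 hours (11.4). UADE and FDA safety reporting follow regulation (11.5). The CEC reviews these events without a period limit (12.1). Section 9.11 states: "Any episode of DKA or severe hypoglycemia will result in withdrawal of subject from study". The DMC must review the in-clinic data before ages 2-6 proceed (12.2), and the sponsor can suspend at its discretion (16.10).
- *That 37-49% of events would be missed.* The documents give no event rate.
- *That sites would apply the count differently.* Under 9.12 a site only notifies the sponsor, and the CEC only recommends.
- *That a definite share of Digital Twin exposure is lost in the interim period.* This would require recommended settings to stay in the pump through an interval the protocol calls a wash-out. The protocol text does not say whether they do.

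**Conclusion.** The point holds as a wording defect in operative safety text, of minor severity. Taken literally, the two clocks and the suspension count leave out 30 to 37 days of Auto Mode use before Visit 11 (about 37-49% of calendar days from Visit 3 to end of phase in Cohort A, 38-47% in Cohort C), the missed-bolus run-in of Challenge #2, the in-clinic study for ages 2-6 and any wash-out. For DKA and severe hypoglycemia those shares apply if algorithm-related includes AHCL. For UADEs the restriction applies on either reading.

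The shares assume that the study period ends at the end-of-phase visit, that a single pass is made, and that visits stay within their windows. The separate visit details spreadsheet was not available. Confidence is medium, because whole-study intent is likely and the sponsor may already apply the rule that way.

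**What to change.** In section 9.12 and the synopsis, replace the opening phrase with: *From enrollment to the subject's last visit, including the run-in, the in-clinic observational study, the study period and any interim period*. Leave the thresholds of 2 and 4 unchanged. If a window from Visit 11 really is intended, state that and give the reason. Separately, ask the sponsor to confirm whether algorithm-related in 9.12 includes AHCL, in line with 12.1; the wording change does not depend on the answer.

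The cost is one phrase in two places by amendment, with no new data or visits. The downside is that the same thresholds would cover more time. Counting only from Visit 3, in one pass, the added calendar days are 30/52 = 58% to 37/38 = 97% of the literal window in Cohort A, and 30/49 = 61% to 37/42 = 88% in Cohort C. These are not all Auto Mode days, since the Challenge #1 example schedule has one Manual Mode day a week. Suspension could come earlier, and a few more events may need the 72-hour notice and 10-day review. If the sponsor already applies the rule throughout, practice does not change.
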